9.2.2 Inclusion Criteria

The eligibility criteria for patients enrolled in the PER are:

- Adult (≥18) pregnant females exposed to lomitapide at any time within 30 days prior to first day of the LMP or during pregnancy.
- Patients who have the ability to understand the requirements of the study.
- Patients who have provided written consent for participation.

A patient may first provide oral consent on a recorded line if she is enroling herself. The CC will then send the patient a consent form for signature, to be returned in a provided postage-paid envelope. Following completion of oral consent, collection of enrolment data will proceed. If a physician obtains informed consent, the physician will indicate to the CC that verbal consent was obtained. The physician will then be sent a consent form for completion by the patient at her next visit.

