9.2.4 Prospective and Retrospective Pregnancy Definitions

In order to reduce the bias that may occur when outcome information is known prior to enrolment, eligible women are advised to enrol in the PER as soon as their pregnancy is known, preferably in the first trimester before the condition of the foetus has been assessed through prenatal testing. In order to determine the impact of such a bias, pregnancy reports and outcomes will be classified as either prospective or retrospective and will be analysed separately.

Confidential Page 21 of 54

The criteria for prospective pregnancies are:

Prospective pregnancies will include patients who are enrolled after exposure to lomitapide but before the outcome of the pregnancy is known. An exception will be made that women who have undergone prenatal testing that could provide knowledge of the outcome of pregnancy will be considered as a prospective report if the outcome of the testing is normal.

Note: Because early prenatal testing is so prevalent, it may be difficult to achieve adequate numbers of prospectively identified patients if all pregnancies with prior prenatal testing are excluded from the prospective analysis. Therefore, the primary analysis includes pregnant women enroled prior to outcome but after a prenatal test as long as the test does not indicate an abnormality. However, this practice could potentially bias the results by lowering the overall risks of birth defects. To examine this possible source of bias, the analysis will also be conducted excluding the subgroup of women who reported negative prenatal testing at the time of enrolment.

All other patients will be counted as retrospective pregnancies.

The retrospective and prospective pregnancies will be collected in a similar fashion, but treated separately as part of any analyses or reports.

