9.3.4.1.2 Enrolment Procedures

Reporting of pregnancy exposures to lomitapide is voluntary. Pregnancies should be reported as early as possible, before prenatal testing has been performed.

The CC will maintain toll-free telephone lines and toll-free faxes to facilitate patient enrolment, data collection, and data queries.

The PER participants will originate from the following sources:

- Patient self-referral through telephone contact with the CC (US and other countries where permissible)
- Prescriber or other HCP referrals
- Pregnancies reported to Aegerion directly from countries where LOWER is ongoing

Confidential Page 25 of 54

9.3.4.1.2.1 Countries Allowing Direct Patient and HCP Contact

9.3.4.1.2.1.1 Direct Patient Reports

In countries, such as the US, that allow for direct patient reports, the CC will explain the purpose and scope of the PER to the patient, obtain verbal consent for participation (if consent has not already been obtained by the HCP), and send the patient a Consent Form, Release of Medical Information (RMI) form and a PER Information Sheet. In some cases, the CC will send information to the patient's HCP as an intermediary. Enrolment data will be collected at the time of the initial report; however, no additional data will be collected until the patient has returned the signed consent form to the CC.

9.3.4.1.2.1.2 Reports from HCPs

HCPs will explain the purpose and scope of the PER to the patient, obtain her consent for participation, and notify the CC. The CC will complete the patient enrolment form, or send it to the HCP for completion. The CC will also provide the HCP with a Consent Form and an RMI form to be completed by the patient and returned to the CC (for obtaining information from other HCPs if necessary) and a PER Information Sheet.

9.3.4.1.2.2 Countries Allowing Only HCP Contact

Unless allowed by national and local regulation, there will be no direct reports from patients.

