9.5 Study Size

HoFH is an ultra-rare disease. The prevalence of defects in both alleles of the LDL-R (homozygous) has been calculated to occur in ∼1 in 1 million persons based on the estimated prevalence of 1 in 500 for the more common heterozygous FH, which is characterised by less severe hypercholesterolaemia.

Every attempt will be made to recruit eligible participants to this PER using methods found to be effective in similar pregnancy exposure registries. However, the number of women who will be candidates for inclusion with an eligible pregnancy cannot be accurately estimated.

Any pregnancies reported in previous clinical studies with HoFH or spontaneous or literature reports of pregnancies with known outcomes will be considered retrospective reports and will be included in the PER and analyzed separately. Any prospective pregnancies reported spontaneously (i.e., from patients not enrolled in the PER) will be handled by the Aegerion Safety Department or its designee. These reports will be included in a pooled analysis of all reports.

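### Prospective status is fixed at an inconsistently defined enrolment, not at first report, so an abnormal prenatal result in any gap between the two lowers the prospective defect rate

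*Protocol*

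**What the plan says.** **Classification (Protocol 9.2.4).** "Prospective pregnancies will include patients who are enrolled after exposure to lomitapide but before the outcome of the pregnancy is known". A woman tested before enrolment "will be considered as a prospective report if the outcome of the testing is normal". Then: "All other patients will be counted as retrospective pregnancies". The protocol concedes that "this practice could potentially bias the results by lowering the overall risks of birth defects", and plans a check: "the analysis will also be conducted excluding the subgroup of women who reported negative prenatal testing at the time of enrolment".

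**Enrolment.** One inclusion criterion in 9.2.2 is "Patients who have provided written consent for participation", and 9.2.3 excludes women who do not give it. The same section starts enrolment data collection once oral consent is complete. When a physician obtains consent, verbal consent is notified first and the form is signed at a later visit. For direct patient reports, 9.3.4.1.2 takes enrolment data at the initial report, after which "no additional data will be collected until the patient has returned the signed consent form to the CC". Section 10.1 follows the same order. Section 9.3.4.1.2 also lists pregnancies reported directly to the sponsor as a source of participants.

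**Use of the term in 9.5.** "Any pregnancies reported in previous clinical studies with HoFH or spontaneous or literature reports of pregnancies with known outcomes will be considered retrospective reports". The next sentences call some spontaneously reported pregnancies of women not enrolled in the registry prospective, and send them to the pooled analysis.

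**The concern.** Separating prospective from retrospective reports is meant to keep knowledge of the outcome from influencing which pregnancies enter the prospective set. What is known at first report serves that purpose. What is known at a later enrolment date serves it less well, because the test result itself can then decide the class.

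The protocol leaves room for such a gap in three places: reports made to the sponsor, HCP reports where the enrolment form is sent out for completion, and every route if the signed form is what marks enrolment. Two coordinators could date the same enrolment weeks apart and classify the pregnancy differently.

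The direction matters. Section 9.7.2 compares the observed defect proportion with external rates to judge the evidence against an elevated risk, and section 7 reports teratogenicity in animals. A rate biased low would reassure wrongly. Section 7 also expects few pregnancies, so a single reclassified case can change the result visibly.

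**Working it through.** The protocol gives no expected defect rate, sample size or lag between report and enrolment, so there is no figure of its own to reproduce.

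**Step 1: the rule applied to a gap.** Take a pregnancy first reported with nothing known about the foetus, and tested before enrolment.

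- Normal result: prospective, by the exception in 9.2.4.
- Abnormal result: retrospective, by the residual clause.
- Pregnancy ended, outcome known: retrospective, whether the outcome was good or bad.

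Only the first two form an asymmetric pair, and they drive the bias in the defect rate.

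**Step 2: where a gap can exist.**

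| Route | Oral consent marks enrolment | Signed form marks enrolment |
|---|---|---|
| Direct patient report | essentially none | until the form is returned |
| HCP report | possible if the enrolment form is sent out | until the form is completed and returned |
| Report to the sponsor | possible | possible |

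**Step 3: illustrative size.** All inputs are assumptions:

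- p = true defect risk among pregnancies reported before outcome (3% or 6%)
- g = share with a prenatal test between first report and enrolment, unrelated to defect status (0 to 0.5)
- s = share of defects that the test flags (0.3 to 0.8)

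With the enrolment anchor, flagged pregnancies leave both numerator and denominator:

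rate = p(1 − g·s) / (1 − p·g·s)

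With the first-report anchor the rate is p. Example with p = 0.03, g = 0.3, s = 0.8: p·g·s = 0.0072, and (0.03 − 0.0072)/(1 − 0.0072) = 0.0228/0.9928 = 2.30%.

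Results for p = 3%:

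| g | s = 0.3 | s = 0.5 | s = 0.8 |
|---|---|---|---|
| 0 | 3.00% | 3.00% | 3.00% |
| 0.1 | 2.91% | 2.85% | 2.77% |
| 0.3 | 2.74% | 2.56% | 2.30% |
| 0.5 | 2.56% | 2.27% | 1.82% |

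The relative understatement for g = 0.1 to 0.5 runs from 3% (2.91/3.00) to 39% (1.82/3.00). For p = 6% the rates run from 5.83% to 3.69%, nearly the same relative range. With g = 0 there is none.

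The model counts risk per pregnancy. The primary measure in 9.7.2 divides by live births and takes affected losses only from 20 weeks. A flagged pregnancy that ends before 20 weeks is therefore outside the primary numerator under either anchor, and the effect on the primary rate is smaller to that extent.

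**Step 4: the planned sensitivity analysis.** Dropping the normal-test women as well leaves p(1 − g)/(1 − g) = p, so in this model it removes the prenatal-test part. That requires normal tests in the gap to be recorded as known at enrolment. If the signature marks enrolment but the data date from the initial report, such a test may not be recorded. The analysis does not bring back pregnancies that ended in the gap.

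**Step 5: small counts.** One affected pregnancy in 20 is 5.0% (exact 95% CI 0.1% to 24.9%). Move that one and the result is 0/19 = 0% (0% to 17.6%).

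**The case against.** The strongest reply is that enrolment already means oral consent with enrolment data. Sections 9.2.2, 9.3.4.1.2 and 10.1 all put oral consent first, and no section says that the date of the signature decides the class. On that natural reading a woman who consents orally, then has an abnormal scan, then signs, stays prospective. This stands for direct patient reports. It does not settle sponsor-reported pregnancies or HCP reports where the form is sent out, and the protocol never states the reading.

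The normal-test exception is also disclosed and has its own sensitivity analysis. Reclassified participants still appear in the retrospective and combined analyses (9.7). Both points stand and limit the harm.

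A reader might infer more than the text supports:

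- *That pregnancies reported before outcome generally become retrospective.* They do so only if the outcome or an abnormal test becomes known in the gap. Section 9.5 still calls early spontaneous reports from women who are not enrolled prospective.
- *That only adverse outcomes are moved.* A healthy live birth known before enrolment is moved too.
- *That early losses bias the primary defect rate.* Losses with no detected defect are excluded (9.7.1), and affected losses before 20 weeks enter only the secondary analysis (9.7.2).
- *That reports from previous clinical studies show the same selection.* Section 9.5 makes them retrospective whatever the outcome, its sentence refers to known outcomes, and the protocol does not show that any such pregnancy was followed prospectively.

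**Conclusion.** The point holds as a defect of definition with a known direction and an unknown size. Enrolment is not fixed consistently, and 9.5 uses prospective in a sense that 9.2.4 does not allow. Wherever report precedes enrolment, the test result can decide the class, and the prospective defect rate can be biased low.

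The bias is 0% where the two dates coincide. The 3% to 39% range rests wholly on assumed values of p, g and s and shows scale only. The planned sensitivity analysis covers the prenatal-test part if tests in the gap are recorded. What it cannot repair is pregnancies that ended in the gap, and these affect mainly the secondary defect analysis and the reported proportions of pregnancy losses. The wording should be changed, but the documents do not show that the primary result will be materially wrong.

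**What to change.** 1. In 9.2.4, classify by whether the outcome or an abnormal prenatal result was known at the date of first report to the CC or the sponsor. The date of initial contact is already a data element in 9.4.
2. In 9.2.2 and 9.3.4.1.2, state that oral consent with enrolment data marks enrolment, and that written consent is still required before further data are collected.
3. In 9.5, bring the use of prospective into line with 9.2.4, or give reports from women who are not enrolled a different name.
4. Report the number of women who gave oral consent but never returned the form, separately and alongside the lost-to-follow-up proportion. They do not meet 9.2.2 and should not enter the rates.

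The cost is mostly wording. First-report dates must be checked for sponsor-reported pregnancies, since 9.4 does not say that its date covers that route. Women who consent after the outcome is known should be flagged, because that consent may itself depend on the outcome, and a sensitivity analysis should be run without them.

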9.3 Variables

The primary outcomes of interest are major congenital abnormalities. Also reported will be pregnancy outcomes, such as induced abortion and foetal loss; the plans for classifications of these outcomes are given below. The PER's definition of pregnancy losses and birth defects is consistent with that used in the Metropolitan Atlanta Congenital Defects Program (MACDP) (National Center for Birth Defects and Developmental Disabilities, 2004). All pregnancy outcomes will be reviewed based on earliest exposure to lomitapide.

9.3.1 Pregnancy Outcomes

Pregnancy outcomes will be classified into one of the following mutually exclusive categories: spontaneous abortion/miscarriage; induced abortion; foetal death/stillbirth; or live birth. Other PER outcomes of interest are: ectopic pregnancy; maternal death; and neonatal death. The PER will attempt to assess all outcomes for the presence of birth defects.

Confidential Page 22 of 54

9.3.1.1 Spontaneous Abortion/Miscarriage

The PER defines any loss of a foetus due to natural causes at less than 20 weeks gestation (with gestational age measured from the first day of the LMP) as a spontaneous abortion. If available, data from gross or pathological examination of the abortus or foetus will be evaluated for structural or chromosomal defects.

9.3.1.2 Induced Abortion

The PER defines an induced abortion as any induced or voluntary foetal loss during pregnancy. If available, data from gross or pathologic examination of the abortus or foetus will be evaluated for structural or chromosomal defects.

9.3.1.3 Foetal Death/Stillbirth

Foetal death or stillbirth refers to foetuses born dead at \geq 20 weeks gestation or weighing \geq 500 g. Foetal death occurring at \geq 20 weeks, but <28 weeks gestation is considered an early foetal loss. Foetal death occurring at \geq 28 weeks is considered a late foetal loss. If available, data from gross or pathologic examination of the abortus or foetus will be evaluated for structural or chromosomal defects. The PER will make the final classification between foetal death/stillbirth and spontaneous abortion based on gestational age and weight. If these parameters are not available, the PER will accept the classification indicated by the HCP.

9.3.1.4 Live Birth

A live birth refers to a complete expulsion or extraction from its mother of a surviving neonate breathing or showing any other evidence of life, such as heartbeat, umbilical cord pulsation, or definite movement of voluntary muscles, whether the umbilical cord has been cut or the placenta is attached.

9.3.1.5 Ectopic Pregnancies

Any reported ectopic pregnancy will be sub-classified in the respective pregnancy outcome including induced abortion, maternal death, live birth, or spontaneous pregnancy loss.

9.3.2 Birth Defects

The PER adopts the term "birth defect" for an abnormality usually referred to as "congenital abnormality." A description of the definition of birth defects is provided in Annex 3.

Confidential Page 23 of 54

9.3.2.1 Major Birth Defects

Criteria for major birth defects will be those used in the MACDP. The MACDP defines a case as one having at least 1 major structural birth defect or syndrome. It uses a defect collection and coding system known commonly as "BPA" codes that was established by the British Paediatric Association (BPA), World Health Organization, and modified by the CDC (National Center for Birth Defects and Developmental Disabilities, 2004). The system is divided into "codable" and "conditional" defects. Codable defects are usually significant structural malformations or genetic syndromes. Additional details are provided in Annex 3.

9.3.3 Effectiveness of Risk Minimisation

Measures of the effectiveness of risk minimisation such as rates of prescribing of contraceptives for women of reproductive potential will be estimated from the companion lomitapide observational cohort study (LOWER). The lomitapide Registry will provide estimates of the types and rates of contraceptive use among women of reproductive age who are being treated with lomitapide. In addition, the lomitapide PER will provide the distribution of self-reported methods of contraception among the women who are PER participants.

9.3.3.1 Pregnancy Root Cause Analysis

A pregnancy root cause analysis (PRCA) will be conducted for every pregnancy that is reported to the PER. Questionnaires will seek to better understand the circumstances of the pregnancy and the patient's and/or HCP's knowledge of the information in the product label concerning pregnancy and the importance of birth control. The PRCA will be conducted with the HCP or, in countries where this is permissible, directly with the patient.

CC staff will use a standardised questionnaire to document the patient's use of birth control and her receipt of information about lomitapide, including the risk of teratogenicity and the need to use highly reliable birth control and possible loss of effectiveness of oral contraceptives due to diarrhoea or vomiting and need for additional contraception. This information, together with other metrics, will be used to determine whether changes need to be made to processes and educational materials to make them more effective in minimising the risk of teratogenicity.

9.3.4 Data Collection

Data collection and entry in the EDC system will be done by the PER CC. Data collection forms are designed to gather data needed for the study that have been documented as part of usual care

Confidential Page 24 of 54

of the patient. If the HCP is unable or unwilling to provide the necessary data over the phone, a hard copy form will be sent to the HCP office for completion and return faxing to the CC.

9.3.4.1 Data Collection Details

9.3.4.1.1 PER Awareness

Active outreach will occur to solicit reports of women exposed to lomitapide during pregnancy. The CC will use various options to make HCPs and patients aware of the PER, such as:

- Discussion by the enroling physician of the PER with female patients of reproductive potential during enrolment in LOWER
- Reminder to physicians participating in the lomitapide Registry to encourage their patients who become pregnant to join the PER, i.e., including eligible patients not enrolled in the lomitapide Registry
- Reminder to prescribers who enrol patients in any lomitapide Named Patient or Compassionate Use/Expanded Access Programs
- Notification of all prescribers of lomitapide where known
- Where appropriate, reference to the PER in product labeling aimed at prescribers and patients
- Notification of HoFH education and support groups
- FDA pregnancy registry website
- Toll-free telephone number printed on applicable patient materials

9.3.4.1.2 Enrolment Procedures

Reporting of pregnancy exposures to lomitapide is voluntary. Pregnancies should be reported as early as possible, before prenatal testing has been performed.

The CC will maintain toll-free telephone lines and toll-free faxes to facilitate patient enrolment, data collection, and data queries.

The PER participants will originate from the following sources:

- Patient self-referral through telephone contact with the CC (US and other countries where permissible)
- Prescriber or other HCP referrals
- Pregnancies reported to Aegerion directly from countries where LOWER is ongoing

Confidential Page 25 of 54

9.3.4.1.2.1 Countries Allowing Direct Patient and HCP Contact

9.3.4.1.2.1.1 Direct Patient Reports

In countries, such as the US, that allow for direct patient reports, the CC will explain the purpose and scope of the PER to the patient, obtain verbal consent for participation (if consent has not already been obtained by the HCP), and send the patient a Consent Form, Release of Medical Information (RMI) form and a PER Information Sheet. In some cases, the CC will send information to the patient's HCP as an intermediary. Enrolment data will be collected at the time of the initial report; however, no additional data will be collected until the patient has returned the signed consent form to the CC.

9.3.4.1.2.1.2 Reports from HCPs

HCPs will explain the purpose and scope of the PER to the patient, obtain her consent for participation, and notify the CC. The CC will complete the patient enrolment form, or send it to the HCP for completion. The CC will also provide the HCP with a Consent Form and an RMI form to be completed by the patient and returned to the CC (for obtaining information from other HCPs if necessary) and a PER Information Sheet.

9.3.4.1.2.2 Countries Allowing Only HCP Contact

Unless allowed by national and local regulation, there will be no direct reports from patients.

9.3.4.2 PER Contact Schedule

In countries that allow contact with the patient and the HCP, during the course of the pregnancy the CC will contact the patient once per trimester. In countries with contact restricted to HCPs, during the course of the pregnancy the CC will contact the patient's HCP once per trimester.

Regardless of country of origin of the report, the patient's HCPs will be contacted at 6 to 7 months of gestation for the Prenatal Follow-Up and within 4 weeks after the EDD for Pregnancy Outcome Follow-Up. The infant's HCP will be contacted by the enroling HCP or by the CC when the infant is 12 weeks of age and at 12 months of age for paediatric follow-up.

The data collection schedule is outlined in Table 1 and Table 2.

Confidential Page 26 of 54

Table 1: Data Collection Schedule in Countries with Data Collection Restricted to HCPs

DATA COLLECTION	REGISTRATION BY LOMITAPIDE PRESCRIBER WITH CC	CC CONTACT WITH THE HCP AT EACH TRIMESTER	6 TO 7 MONTHS OF GESTATION FOR THE PRENATAL FOLLOW- UP	CC CONTACT WITH PRACTITIONER(S) AT THE PREGNANCY OUTCOME FOLLOW- UP WITHIN 4 WEEKS AFTER THE EDD	HCP OR CC CONTACT WITH THE INFANT'S HCP AT THE PAEDIATRIC FOLLOW-UP AT 12 WEEKS OLD AND 12 MONTHS OLD ¹
Consent	X				
Patient Demographics and Pregnancy History	X				
Lomitapide Use	X	X	X	X	X (if mother is nursing)
Concomitant Medications	X	X	X	X	X
Medical History	X				
Pregnancy Outcome				X	
Paediatric History and Examinations				X	X
Serious Adverse Events (Pregnancy-Related)		X	X	X	X

¹ The 12-week follow up should be conducted +/- one week.

Confidential Page 27 of 54

Table 2: Data Collection Schedule in Countries with Data Collection from Patients or HCPs

DATA COLLECTION	REGISTRATION/ ENROLMENT	CC CONTACT WITH THE PATIENT AT EACH TRIMESTER	CC CONTACT WITH THE PATIENT'S HCP(S) AT THE PRENATAL FOLLOW- UP, 6 TO 7 MONTHS OF GESTATION	CC CONTACT WITH THE HCP(S) AT THE PREGNANCY OUTCOME FOLLOW- UP ¹ WITHIN 4 WEEKS AFTER THE EDD	CC CONTACT WITH THE INFANT'S HCP AT THE PAEDIATRIC FOLLOW-UP AT 12 WEEKS AND 12 MONTHS OLD ^{2,3}
Consent ⁴	X				
Patient Demographics and Pregnancy History	X				
Contact Information	X	X	X		
Lomitapide Use	X	X	X	X	X (if mother is nursing)
Concomitant Medications	X	X	X	X	X
Medical History	X				
Pregnancy Status/ Outcome		X	X	X	
Paediatric History and Examinations				X	X
Serious Adverse Events (Pregnancy Related)		X	X	X	X

Confidential Page 28 of 54

The CC will contact the patient's HCP earlier in the pregnancy for outcome data if the patient reports an adverse pregnancy outcome or an induced abortion.
 The CC will contact the infant's HCP. The HCP will be designated either at registration/enrolment or during one of the previous collection time periods.
 The 12-week follow up should be conducted +/- one week.
 The CC will first obtain verbal informed consent. The CC will then mail the patient a Consent Form and Release of Medical Information form to sign and return.

